8.3. Analysis Methods

8.3.1. Primary Efficacy Analyses

The primary endpoint is the proportion of subjects who experience worsening of asthma by Week 24 as defined by at least one of the following:

- On 2 consecutive days, AM PEF \leq 75% of mean AM PEF measured over the last 7 days of the Run-in
- $FEV_1 < 80\%$ of baseline (Visit 2)
- Increase in rescue medication use of ≥ 6 puffs/day on 2 consecutive days compared to mean use over the last 7 days of the Run-in
- Increase in ACQ-5 score of ≥ 0.5 compared to baseline (Visit 2)
- The occurrence of a severe asthma exacerbation (asthma attack) defined as deterioration of asthma that leads to the use of systemic corticosteroids for at least 3 days, hospitalization, or an Emergency Department visit

Logistic regression modeling will be used to compare each GB001 group with placebo. The model will include covariates for treatment group, ICS dose (medium or high) at randomization, region (North America, Eastern Europe, Western Europe), baseline pre-bronchodilator FEV₁, and baseline ACQ-5 score. If the full model does not converge, a model with treatment group, ICS dose at randomization, and region as covariates will be utilized. If this reduced model does not converge, a model with treatment group and ICS dose at randomization will be used. In the rare case that convergence issues remain, only treatment group will be included in the model.

The number and proportion of subjects meeting the primary endpoint and corresponding 95% Wilson (Score) CIs (Wilson, 1927) will be summarized by treatment group. ORs, corresponding asymptotic 95% CIs along with the absolute differences and corresponding 95% CIs, and p-values will be summarized for each GB001 group versus placebo. The 95% CIs for the absolute difference will be Newcombe continuity-corrected CIs (Newcombe, 1998). Percentage reductions and corresponding 95% CIs will also be summarized. Lastly, the number and proportion of subjects meeting each component of the primary endpoint, with observed worsening of asthma, and with an assigned status of asthma worsening will also be summarized by treatment group. Subjects can meet more than one component of the primary endpoint.

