8.3.1.1.4. Sensitivity Analysis #4: Multiple Imputation

If the number of subjects overall with a missing observed status for asthma worsening by Week 24 is \geq 5%, then the following MI approach will be conducted as a sensitivity analysis.

The dichotomous outcome of asthma worsening by Week 24 will be imputed for subjects who have withdrawn from study without having experienced asthma worsening using a MI approach assuming that these subjects with a missing dichotomous outcome would have similar outcomes to subjects who had an observed status of asthma worsening by Week 24. The dichotomous outcome will be imputed directly as opposed to imputing the individual components of the primary endpoint and then deriving the composite outcome.

The following steps will be performed:

- Intermittent missing values will first be imputed using the Fully Conditional Specification method, which is appropriate for non-monotonic missing data for binary data.
- The monotone missing values will then be multiply imputed using the monotone logistic regression imputation method (Allison, 2005). A monotone missing pattern is such that in the event that a variable is missing it is implied that all subsequent variables are also missing (i.e. once a subject withdraws from study, no additional data is expected for that subject).
- For each stage, MI will be performed within treatment group with covariate adjustment the same as the primary analysis of the primary endpoint and non-missing outcomes for asthma worsening. Should convergence issues occur due to small cell size for the categorical covariates at either stage, they will be removed from the model.
- The primary analysis of the primary endpoint as described in Section 8.3.1 will be performed for each complete, imputed dataset.
- Fifty imputations will be performed.
- Results of the logistic regression on the multiple imputed data sets will be combined to generate an overall estimate and associated variance using Rubin's rules (Rubin, 1987).

The imputed data logistic regression model-based estimates of the proportion of subjects with asthma worsening, ORs, corresponding 95% CIs, and p-values will be reported. Percentage reductions and corresponding 95% CIs will also be provided.

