If a given analysis fails to converge due to the complexity of model specification, the following will be considered to enable model convergence: 1) use of maximum likelihood estimation instead of REML; and/or 2) a compound symmetric or first-order autoregressive covariance structure will be utilized, based on the covariance structure converging to better fit as determined based on Akaike's information criterion (Akaike, 1973).

Actual values and change from baseline values for ACQ-5 score, pre-bronchodilator FEV₁, postbronchodilator FEV₁, and AM PEF will be summarized by visit. Differences in means, SEs, and corresponding 95% CIs constructed from analysis of variance (ANOVA) models adjusting for treatment group only will also be presented. In addition, figures of mean actual values and mean change from baseline values, including SE bars, for ACQ-5 score and pre-bronchodilator FEV₁ by visit will be provided. Lastly, bar graphs of the LS means and CIs for Week 24 for ACQ-5 score and pre-bronchodilator FEV₁ will be provided.

Lastly, a sensitivity analysis with a different method of handling pre-bronchodilator FEV₁ measurements confounded by systemic corticosteroid use will be performed. Pre-bronchodilator FEV₁ measurements collected from systemic corticosteroid start date to systemic corticosteroid end date + 14 days will be excluded in order to reduce the confounding effect of systemic corticosteroids. If the number of subjects overall with a missing change from baseline is < 5%, then only ANCOVA without MI will be performed. If the number of subjects overall with a missing change from baseline value is \geq 5%, ANCOVA with MI and MMRM with MI will be performed.

ACQ-5 score, pre-bronchodilator FEV₁, post- bronchodilator FEV₁, and AM PEF data will also be presented in by-subject data listings.

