8.3.2.3. Annualized Rate of Severe Asthma Exacerbations

A severe asthma exacerbation is defined as deterioration of asthma that leads to the use of systemic corticosteroids for at least 3 days, hospitalization, or an Emergency Department visit. Exacerbations for which the courses of systemic corticosteroids are separated by 7 or more days will be counted as separate severe asthma exacerbations.

The number and proportion of subjects with 0, 1, and ≥ 2 severe exacerbations and the annualized rate of severe asthma exacerbations will be summarized. The unadjusted annualized rate of severe exacerbations will be calculated as the total number of severe exacerbations divided by the total number of subject-years of follow-up and will also be summarized.

The total number of severe exacerbations will be analyzed using a negative binomial regression model, with the logarithmic transformation of follow-up time as the offset parameter. The follow-up time is defined as the subject's time on study up to and including Day 174. The model will include terms for treatment group, ICS dose (medium or high) at randomization, region, age at screening, and the number of exacerbations in the past 12 months. If the distribution of severe exacerbation data is under dispersed, or if the negative binomial regression model fails to converge, a Poisson regression model will be used instead of the negative binomial regression model. Exacerbations for which the courses of systemic corticosteroids are separated by 7 or more days will be counted as separate exacerbations.

Rate ratios for each GB001 group versus placebo, corresponding 95% CIs, and p-values will be provided from the model. In addition, the rate ratios and corresponding 95% CIs for the 3 pairwise comparisons among each of the GB001 treatment groups will be provided (60 mg vs 20 mg, 60 mg vs 40 mg, 40 mg vs 20 mg). Lastly, percentage reductions and corresponding 95% CIs will also be provided.

A sensitivity analysis will be performed to include asthma exacerbations that were treated with an intramuscular (IM) injection of systemic corticosteroids for less than 3 days. In this analysis, a severe asthma exacerbation will be defined as deterioration of asthma that leads to the use of oral or intravenous systemic corticosteroids for at least 3 days, the use of IM systemic corticosteroids for at least 1 day, hospitalization, or an Emergency Department visit.

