8.4. Examination of Subgroups

Subgroup analyses of the primary and two secondary (ACQ-5 score and pre-bronchodilator FEV₁) efficacy endpoints will be performed for all of the subgroups specified below. In addition, subgroup analyses of the secondary efficacy endpoint of annualized rate of severe asthma exacerbations will also be performed for select subgroups as specified below. For any subgroup level that does not comprise $\geq 10\%$ of the ITT population, the analyses based on the models will not be performed. The subgroups of interest are described below.

Demographic and general baseline characteristic subgroups:

- Age (years; $< 65, \ge 65$)
- Sex (male, female)
- BMI (kg/m²; < 30, \geq 30)
- Baseline ICS dose ([per randomization and per actual value]; medium, high, including comparison of GB001 medium to Placebo high)
- Region (North America, Eastern Europe, Western Europe)
- Total number of exacerbations in the past 12 months (1, > 1)

Efficacy-related baseline characteristic subgroups:

- Pre-bronchodilator percent predicted FEV₁ at Screening (%; $< 60, \ge 60$)
- ACQ-5 score at Baseline ($< 1.5, \ge 1.5$)

Biomarker baseline characteristic subgroups:

- Blood eosinophils at Baseline (GI/L; < 0.20, ≥ 0.20; < 0.25, ≥ 0.25 [including for annualized rate of severe asthma exacerbations]; < 0.30, ≥ 0.30)
- FeNO at Baseline (ppb; < 25, ≥ 25 [including for annualized rate of severe asthma exacerbations]; < 30, ≥ 30; < 35, ≥ 35; < 50, ≥ 50)
- Blood eosinophils and FeNO at Baseline ([blood eosinophils < 0.25 GI/L and FeNO < 25 FeNO ppb] vs [blood eosinophils ≥ 0.25 GI/L and/or FeNO ≥ 25 ppb] {including for annualized rate of severe asthma exacerbations}; repeat for 0.25 vs 30, 0.25 vs 35, and 0.25 vs 50)
- Blood eosinophils and FeNO at Baseline ([blood eosinophils < 0.25 GI/L and FeNO < 25 FeNO ppb] vs [blood eosinophils < 0.25 GI/L and FeNO ≥ 25 ppb] vs [blood eosinophils ≥ 0.25 GI/L and FeNO < 25 ppb] vs [blood eosinophils ≥ 0.25 GI/L and FeNO < 25 ppb] vs [blood eosinophils ≥ 0.25 GI/L and FeNO < 25 ppb] vs [blood eosinophils ≥ 0.25 GI/L and FeNO > 25 ppb]; including for annualized rate of severe asthma exacerbations)
- IgE (IU/mL; normal [≤ 158], high [> 158])
- 25-Hydroxyvitamin D at Baseline $(ng/mL; \leq 20, > 20)$
- Chloride at Baseline (mmol/L; ≤ Quartile 1, > Quartile 1-≤ Quartile 2, > Quartile 3-≤ Quartile 3, > Quartile 3, where quartiles are based on the ITT population)

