Models used for the subgroup analyses will be the same as those used for the primary and secondary efficacy endpoints as specified in Section 8.3.1 and Section 8.3.2.1 with covariates for the subgroup (if different than the aforementioned covariates i.e. baseline ICS dose (medium or high) at randomization and region; for the efficacy-related baseline characteristic subgroups, baseline pre-bronchodilator FEV_1 or baseline ACQ-5 score will be replaced with a categorical subgroup variable) and treatment group by subgroup interaction added. If the model does not converge, a reduced model including only treatment group, ICS dose at randomization, and region will be used.

Heterogeneity of treatment effect across different levels of each subgroup will be evaluated by presenting p-values for the treatment by subgroup interaction. The interaction term tests whether the treatment effect is significantly different across different levels of the subgroup, between males and females, for example. If a subgroup variable has more than two levels then the least severe level (where applicable) will be used as the reference subgroup, and the test will assess whether the treatment effect in the more severe levels differs from that in the reference subgroup.

Forest plots of the treatment effect estimates and corresponding 95% CIs from the subgroup analyses will be provided.

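### The fallback for a non-converging subgroup model drops the treatment-by-subgroup interaction, so it cannot deliver the interaction p-values or subgroup estimates that SAP 8.4 requires

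*SAP*

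**What the plan says.** SAP 8.4 plans subgroup analyses of the primary endpoint, ACQ-5 and pre-bronchodilator FEV1, and of the severe exacerbation rate for selected subgroups. Each model is the endpoint's own model with the subgroup and its interaction with treatment added. On failure, the rule is: "If the model does not converge, a reduced model including only treatment group, ICS dose at randomization, and region will be used".

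The next two paragraphs set the outputs. On heterogeneity: "Heterogeneity of treatment effect across different levels of each subgroup will be evaluated by presenting p-values for the treatment by subgroup interaction". On display: "Forest plots of the treatment effect estimates and corresponding 95% CIs from the subgroup analyses will be provided". Neither makes an exception for subgroups where the fallback was used.

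There is a size limit. For a subgroup level below 10% of the ITT population, "the analyses based on the models will not be performed". The prespecified subgroups include splits with more than two levels: region, chloride quartiles and a four-way eosinophil-by-FeNO classification.

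**The concern.** A fallback for a failed fit should simplify the model around the quantity of interest. Here the quantity of interest is the interaction, and the fallback removes it. Where the rule applies, the analyst gets an overall treatment effect adjusted for two stratification-type covariates. It says nothing about whether the effect differs by subgroup or what it is within a level.

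The biomarker subgroups (eosinophils, FeNO and their combinations) bear on which patients respond, and Protocol 9.5 says the interim results are meant to inform further development of GB001. Followed literally, the rule leaves gaps in the planned tables. If it is not followed, someone must choose a method after seeing unblinded data.

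**Working it through.** **1. Terms in the two models.** With four arms and a subgroup of k levels, the interaction has (4 − 1)(k − 1) = 3(k − 1) degrees of freedom: 3 for two levels, 6 for region and 9 for quartiles or the four-way split. The fallback has 0 in every case.

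**2. The SAP's other convergence rules.**
- Primary model, SAP 8.3.1: "If the full model does not converge, a model with treatment group, ICS dose at randomization, and region as covariates will be utilized". These are the same three terms as in 8.4, but here treatment is the effect of interest, and it stays in at every later step too.
- Multiple imputation, SAP 8.3.1.1.4: "Should convergence issues occur due to small cell size for the categorical covariates at either stage, they will be removed from the model". Imputation is done within treatment group, so treatment is not lost. This sentence also shows that the SAP expects small cells to cause trouble.
- MMRM, SAP 8.3.2.1: "use of maximum likelihood estimation instead of REML", or a simpler covariance structure. The fixed effects stay.
- Exacerbation rate, SAP 8.3.2.3: "if the negative binomial regression model fails to converge, a Poisson regression model will be used instead of the negative binomial regression model". The distribution changes and the terms stay.

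Only 8.4 drops the term being tested, and no other section restores it.

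**3. The planning figure, reproduced (SAP 2.5).** Inputs: 25% on placebo, 10.2% on each GB001 dose, 120 per arm, 8% dropout, two-sided 0.050.
- Odds ratio = (0.102/0.898)/(0.25/0.75) = 0.341, a 65.9% reduction; the plan says 66%.
- n = 120 × 0.92 = 110.4. SE of the log odds ratio = √[1/(110.4 × 0.25 × 0.75) + 1/(110.4 × 0.102 × 0.898)] = 0.384.
- Power = Φ(1.077/0.384 − 1.960) = 80.1%; the plan says 80%.

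The rates are therefore a fair statement of what the plan expects.

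**4. Sparse cells by formula.** A level of m subjects per arm has no events in a GB001 arm with probability (1 − 0.102)^m, and in the placebo arm with probability (1 − 0.25)^m. At the 10% minimum, m = 12, with 12 × 0.102 = 1.2 expected events per GB001 arm. The chance of no events is 0.898^12 = 27% in a given GB001 arm and 0.75^12 = 3% on placebo. At least one of the four cells is empty with probability 1 − (1 − 0.275)^3 × (1 − 0.032) = 63%. For levels of 15%, 20% and 25% (m = 18, 24, 30) this is 38%, 21% and 11%.

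**5. Sparse cells by simulation.** 40,000 four-arm trials per setting, 120 per arm, with level sizes varying at random and every level at least 48 of 480. The table gives the chance of at least one arm-by-level cell with no events or only events. The first four columns are two-level subgroups, headed by the share of one level. The 35%/20% pair is assumed. The last pair comes from the earlier ICS-withdrawal study in Protocol 2.2 (placebo and GB001 20 mg) and is an upper-side scenario.

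| Placebo / each GB001 arm | 15% | 20% | 30% | 50% | Quartiles |
|---|---|---|---|---|---|
| 25% / 10.2% | 40.8% | 23.5% | 7.0% | 1.1% | 42.9% |
| 35% / 20% | 7.7% | 2.2% | 0.2% | 0.0% | 2.6% |
| 52.8% / 20.8% | 6.5% | 1.7% | 0.1% | 0.0% | 2.0% |

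Repeat runs agreed within one percentage point.

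**6. What the models do in those trials.** 1,000 trials were fitted in each of six scenarios: 15% level, 20% level and quartiles, at the first two rate pairs. Assumptions: the same odds ratio in every level, a 50/50 ICS split, three equal regions, and baseline FEV1 and ACQ-5 unrelated to outcome. Trials with a no-event or all-event cell: 401 + 254 + 431 = 1,086 at 25%/10.2% and 89 + 22 + 18 = 129 at 35%/20%, total 1,215 of 6,000.
- The SAP subgroup model was separated in all 1,215 and fitted in the other 4,785.
- With a stop on coefficient change (<1e-6, at most 25 iterations), 1,215 of 1,215 did not converge. With a stop on relative log-likelihood change (<1e-8), 0 of 1,215 were reported as non-converged, yet each had a treatment log-odds-ratio SE of at least 822.
- The fallback fitted in all 1,215, with no subgroup effect in any.
- A Firth-penalised fit of the full subgroup model was finite in all 1,215. It gave an interaction p-value and finite 95% CIs for every dose-by-level effect (6 for two levels, 12 for quartiles).

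**7. Error rate of the remedy.** Another 2,000 trials per scenario with no true interaction, nominal 5%. Wald tests where not separated plus Firth where separated rejected in 2.4–4.0%; likelihood-ratio tests plus Firth in 2.7–6.9%; Firth throughout in 2.2–5.0%.

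**The case against.** The authors may have meant a reduced covariate set with the added subgroup and interaction terms kept, or a fit within each level. The fallback has the same three terms as the one in 8.3.1, and it follows directly after the sentence adding those terms. That is plausible, but the text restricts the model to three named terms. A within-level fit is not described and would still give no interaction p-value. If that was the intent, the sentence still needs correcting.

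The frequency argument is weaker than the percentages suggest, and this stands. The rule is triggered by reported non-convergence, while the simulations count sparse cells. The two assumed stopping rules gave opposite answers, and neither is tied to the SAS procedures the SAP will use. Of the 1,215 affected trials, 1,086 (89%) come from the planning rates, and the fitted runs left out 30% and 50% levels. So 1,215 of 6,000 is not a rate for this trial.

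Three smaller points also stand. Descriptive subgroup counts could still be shown, so what is lost is the model-based result. SAP 8.4 points to the models in 8.3.1 and 8.3.2.1 but not 8.3.2.3, so it is unclear which fallback governs the exacerbation-rate subgroups. And the likelihood-ratio variant exceeds 5% in some scenarios, mainly through ordinary likelihood-ratio tests in non-separated trials, so the test should be named.

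Finally, these are supportive tests without multiplicity adjustment in a Phase 2b trial. That limits the importance of the point without making the rule workable.

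**Conclusion.** The concern holds on the text alone: the fallback has 0 interaction degrees of freedom where 3(k − 1) are needed, and no section repairs this. It should be corrected, but its reach is limited. The primary analysis is untouched. The ACQ-5 and FEV1 ANCOVA models have no iterative convergence step, and MMRM has its own rule. The exposure is mainly the logistic primary endpoint in small or multi-level subgroups.

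On the planning rates, sparse cells would be common there: about 41% for a 15% level, 23–24% for a 20% level and 43% for quartiles. They would be uncommon at higher event rates (8% or less) or for balanced two-level subgroups (about 1% or less). Those figures rest on assumed level sizes (quartiles apart) and assumed true rates, and they are a guide to sparse data rather than a forecast of how often software will report non-convergence.

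**What to change.** Replace the fallback sentence in SAP 8.4 with text to this effect:

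> If the model does not converge or, for the logistic model, shows separation, treatment group, subgroup and their interaction will be retained. For the logistic model, a Firth-penalised fit of the same subgroup model, with penalised-likelihood CIs and interaction p-value, will be used and flagged; if this also fails, baseline FEV1 and ACQ-5 will be dropped first (where not the subgroup variable). For the exacerbation rate, the Poisson rule in Section 8.3.2.3 applies with the interaction retained. If no model can be fitted, the interaction will be reported as not estimable, with event counts by treatment and subgroup level.

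ICS dose and region stay in. Separation must be a trigger in its own right, because some stopping rules report a separated fit as converged. A treatment-by-level cell with no events or only events is a simple check; it identified every separated fit in the runs above. The text should also name the interaction test for ordinary logistic fits. The Wald test, combined with Firth where separated, stayed below 5% in all six scenarios.

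The cost is one SAP sentence and minor programming. The downsides are that some forest-plot rows will use a different, flagged estimator, and that the combined Wald and Firth test is somewhat conservative (2.4–4.0% at a nominal 5%).

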9. SAFETY EVALUATION

9.1. Adverse Events

Verbatim AE terms will be coded to a SOC and PT using the Medical Dictionary for Regulatory Activities (MedDRA) Version 21.0 or later.

All analyses of AEs will be based on the principle of treatment emergence. An AE is considered to be treatment-emergent if it has a start date on or after the date of the first dose of study treatment. In general, if the treatment emergence of an AE is not clear due to a missing or incomplete AE start date, the AE will be considered to be treatment-emergent unless the non-missing portions of the start date and the end date indicate otherwise.

In general, whenever a tabular summary of AEs is mentioned in this document, it is intended that the tabular summary is in reference to TEAEs, even though "treatment-emergent" may not be explicitly mentioned. By-subject data listings of AEs will include all events regardless of treatment emergence and TEAEs will be identified.

Counting will be by subject, not event, and at each level of summarization (e.g., any AE, SOC, and PT), with subjects experiencing more than one AE counted only once. In the summary of AEs by severity (mild, moderate, severe), subjects will be counted once at the highest severity reported at each level of summarization. AEs that are missing severity will be presented in summary tables as "Missing". AEs that are missing relationship to study treatment will be presented in summary tables as "Related".

The following summaries will be presented for the safety population:

- Overall Summary of AEs showing the number and percent of subjects with an AE; a moderate or severe AE; a severe AE; a SAE including asthma worsening-related terms; a SAE excluding asthma worsening-related terms; a treatment-related AE; a treatment-related SAE; an AE leading to discontinuation of study treatment; an AE leading to withdrawal from study; an AE resulting in death; and an AE of interest (as defined in Protocol Section 10.3.3).
- Incidence of AEs by SOC and PT
- AEs with Incidence \geq 5% in Any Treatment Group by PT
- Incidence of SAEs by SOC and PT Including Asthma Worsening-Related Terms
- Incidence of SAEs by SOC and PT Excluding Asthma Worsening-Related Terms
- Incidence of AEs by SOC, PT, and Maximum Severity
- Incidence of Treatment-Related AEs by SOC and PT
- Incidence of AEs Leading to Discontinuation of Study Treatment by SOC and PT
- Incidence of AEs Leading to Withdrawal from Study by SOC and PT
- Summary of Pruritus AEs
- Incidence of Liver Chemistry AEs by PT

- Incidence of Liver Chemistry AEs Leading to Discontinuation of Study Treatment by PT
- Incidence of AEs of Interest by SOC and PT

All AEs, AEs leading to discontinuation of study treatment and/or withdrawal from study, AEs of interest, SAEs, and AEs resulting in death will be presented in by-subject data listings.

